1 SYNOPSIS

Title of Study: A Phase 3 Open-Label Extension Study to Evaluate the Long-Term Safety of Omiganan Topical Gel in Subjects with Rosacea
	

Study Period (Planned): Start –First subject enrolled: [REDACTED] End – Last subject last visit: [REDACTED]
	
Phase of Development: Phase 3

Objectives: To evaluate the long-term safety of omiganan topical gel applied once daily to the face of subjects with papulopustular rosacea
	

Methodology: Open-label, multi-center, long-term safety study
	

Number of Subjects (planned): Up to 300 enrolled, to achieve up to 300 evaluable at 6 months and up to 100 at 12 months
	

Number of Sites: Approximately 35 sites in the United States, Canada, France, Netherlands, United Kingdom, Sweden, Australia and New Zealand.
	

Diagnosis and Main Criteria for Inclusion:
 
 • Male or non-pregnant female subjects at least 18 years of age with severe papulopustular rosacea (IGA score of 4) 	

Investigational Product: Omiganan topical gel Comparator Product: None
 
Dose: Apply once daily (Preferably in the morning), as a thin film, to the entire face (Approximately 0.4 grams) Mode of Administration: Topical application to the entire face avoiding contact with the mouth, eyes and inside the nose Duration of Treatment: Up to 12 months (52 Weeks ± 14 Days)
	

Criteria for Evaluation:
 
Safety: Adverse events (AE) throughout the study at Month 1, 3, 6, 9, 12. Physical exam, vital signs, immunogenicity and safety labs will be collected at select time-points.
 
Statistical Methods: Safety: Adverse events will be categorized by SOC and Preferred Term from the current version of MedDRA. Changes or shifts in safety laboratory data and vital signs be summarized at all time-points when available. Summaries will include means, standard deviations, median, minimum and maximum values for continuous data, or frequency and percent for categorical data. Additionally, shift tables will be provided for abnormal safety labs.
	

CONFIDENTIAL

Version Date: 07 March 2017

3 LIST OF ABBREVIATIONS

LIST OF ABBREVIATIONS	
AE	Adverse Experience/Event
AHA	Alpha hydroxyl acids
ALT	Alanine aminotransferase
AST	Aspartate aminotransferase
BUN	Blood urea nitrogen
CBC	Complete blood count
CLS001	Omiganan topical gel (referred to as omiganan)
DNA	Deoxyribonucleic acid
E. coli	Escherichia coli
eCRF	Electronic Case Report Form
CRO	Contract Research Organization
eDC	Electronic Data Capture
EOT	End of Treatment
FDA	U.S. Food and Drug Administration
gm	Gram
GCP	Good Clinical Practice
GGT	Gamma glutamyl transferase
HDL	High-density lipoproteins
ICF	Informed Consent Form
ICH	International Council on Harmonization
IEC	Independent Ethics Committee
IGA	Investigators Global Assessment

CONFIDENTIAL

Version Date: 07 March 2017

LIST OF ABBREVIATIONS	
IRB	Institutional Review Board
LDH	Lactic dehydrogenase
LDL	Low-density lipoproteins
MedDRA	Medical Dictionary for Regulatory Activities
mg	Milligram
MIC	Minimum Inhibitory Concentration
mm	Millimeter
P. acnes	Propionibacterium acnes
PI	Principal investigator
PK	Pharmacokinetic
QSAD	As much as needed
RBC	Red blood cell
RNA	Ribonucleic acid
S. aureus	Staphylococcus aureus
SAE	Serious Adverse Experience/Event
SAR	Serious Adverse Reaction
SOC	System Organ Class
USP	United States Pharmacopeia
w/w	Weight for weight
WBC	White blood cell

CONFIDENTIAL

Version Date: 07 March 2017

5 INTRODUCTION

5.1 BACKGROUND

Rosacea is a chronic dermatologic disorder that primarily affects the facial skin. An estimated 16 million Americans have rosacea.¹ The prevalence of rosacea in Europe is between 1% and 10% of the adult population.^{2,3} The clinical signs and symptoms of rosacea are: facial flushing, telangiectasia, facial erythema, central facial inflammatory papules and pustules, hypertrophy of the sebaceous glands of the nose and ocular changes.⁴ Rosacea has been classified into four different subtypes:

- Subtype 1: erythematotelangiectatic,
- Subtype 2: papulopustular,
- Subtype 3: phymatous and
- Subtype 4: ocular

Each subtype has severity grades ranging from mild to severe.⁵ The subtypes may share common symptoms and may clinically overlap.

The typical age of onset is from 30 to 50 years of age and it is more common in women than men. However, men are more prone to the phymatous skin changes associated with rosacea. Rosacea patients experience periods of relapses and remissions. There are trigger factors that exacerbate the disease such as: sun exposure, stress, hot or cold weather, alcohol, spicy foods, exercise, wind, hot drinks and certain skin care products and medications.⁶

According to surveys conducted by the National Rosacea Society, more than 76 percent of rosacea patients said this condition had lowered their self-confidence and self-esteem, and 38 percent reported it had caused them to avoid public contact or cancel social engagements. Among those with severe rosacea, nearly 88 percent said the disorder had adversely affected their professional interactions, and nearly 51 percent said they had even missed work because of their condition. Over 80 percent reported medical treatment had improved their emotional and social well-being.⁷

Currently, there is no cure for rosacea and the etiology is poorly understood.⁸ Many theories regarding the cause of rosacea have been highlighted in the literature. The pathology of rosacea may be multifactorial and has several associations still not well understood: abnormal vascular and immune system responses; proliferation of commensal mites seen in hair follicles, *Demodex folliculorum*; bacterial proliferation in the human gut of *Helicobacter pylori*; prolonged topical steroid use and other aggravating trigger factors like sun and stress.^{9,10} Gallo and his colleagues found an abnormally high level of the naturally occurring antimicrobial peptides known as cathelicidins upon histopathological staining of the skin of patients with rosacea.¹¹

CONFIDENTIAL

Version Date: 07 March 2017

Therapeutic approaches for the treatment of rosacea may be categorized by the subtype (1-4).⁵ For example, systemic treatments and ablative therapy are used for erythematotelangiectatic rosacea (Subtype 1). Surgery or laser therapy may be indicated for phymatous rosacea (Subtype 3). Topical or systemic medications may be prescribed for papulopustular and ocular rosacea (Subtype 2 and 4, respectively).

The inflammatory (papulopustular) lesions of rosacea affect both the sebaceous and hair follicles.¹² Inflammatory cells may be key pathophysiologic factors in the development of rosacea.¹³ Intrafollicular neutrophils have been observed in inflammatory rosacea and the proteases released by these neutrophils may degrade extracellular matrix macromolecules.¹⁴

There is no cure for rosacea and treatment is aimed at alleviating the symptoms. Topical or oral medications are generally prescribed for mild to moderate papulopustular rosacea. These topical medications include: metronidazole, azelaic acid, ivermectin, sodium sulfacetamide and sulfur, erythromycin, and tretinoin. Oral medications prescribed for severe disease include doxycycline at microbial and subantimicrobial doses, and minocycline.^{4, 15, 16, 17} Isotretinoin, although not FDA approved for the treatment of rosacea, has also been prescribed when other agents have failed. In particular, treatments for severe rosacea are inadequate, and isotretinoin use has occurred with increasing frequency in this patient population.^{18, 19, 20, 21, 22, 23} Hence, topical Omiganan has the potential to become an important addition to the dermatologist's armamentarium in treating severe rosacea.

Cutanea Life Sciences is developing omiganan topical gel for the treatment of papulopustular rosacea. The exact cause of rosacea is unknown and may be due in part to an inflammatory process. Recent research has shown that cationic peptides such as omiganan may have anti-inflammatory properties and may play a role in inhibiting the inflammatory response.⁹ Omiganan may also prevent the inflammatory cascade that is theorized to lead to the signs and symptoms of rosacea. A possible anti-inflammatory activity of omiganan is suggested by the observation of a reduction in inflammatory acne lesion counts with omiganan in two Phase 2 clinical trials. However, the exact mechanism of action is undetermined.

In general, antimicrobial peptides are believed to act by disrupting the cytoplasmic membrane of bacteria resulting in depolarization and death.^{24, 25, 26, 27} Omiganan, in *in vitro* assays, demonstrated a rapid bactericidal activity against not only *P. acnes*, but also against other microorganisms that colonize the skin and that may play a role in the pathogenesis of inflammatory lesions. Omiganan permeabilized the outer membrane of *E. coli* in a dose-dependent manner but did not permeabilize the inner membrane, at concentration up to 4X MIC. Omiganan induced a dose-dependent depolarization in the cytoplasmic membranes of *S. aureus*.²⁸ In addition, a dose-dependent inhibition of DNA, RNA and protein synthesis in *S. aureus* was produced by omiganan.

CONFIDENTIAL

Version Date: 07 March 2017

[REDACTED]

Omiganan pentahydrochloride topical gel has been evaluated in over 2,500 people in human clinical studies at concentrations of 0.5%, 1.0%, 2.5% and 3% in Phase 1 studies; at concentrations of 1.0%, 1.75% and 2.5% in Phase 2 studies; and at concentrations of 1.0% in a Phase 3 study. Omiganan topical solution for acne has been evaluated at concentrations of 1.0% and 5% in Phase 1 studies, as well as 1.25%, 2.5% and 5% in Phase 2 studies. In these studies, including two Phase 2 studies of omiganan topical gel applied to the face of subjects with moderate to severe papulopustular rosacea, omiganan was found to be safe, and well tolerated. In the most recent Phase 2 study in which vehicle or omiganan pentahydrochloride topical gel 1.0%, 1.75% or 2.5% was applied once daily to the face of 240 moderate to severe rosacea subjects for 12 weeks, the most frequently reported adverse events were headache, sinusitis, and upper respiratory tract infections. Most treatment emergent adverse events were considered mild or moderate in severity.

Additionally, the systemic absorption of omiganan pentahydrochloride topical gel was evaluated at concentrations of 0.5%, 1%, 2.5% and 3%. Omiganan was not systemically absorbed when applied to the skin at concentrations ranging from 0.5% to 3% topical gel. In the most recent maximum use PK study of omiganan pentahydrochloride topical gel 2.5% w/w, applied for 21 days to the face of 26 subjects with moderate to severe papulopustular rosacea, no systemic absorption was detected. The results of the clinical studies and the safety data collected during the clinical studies of omiganan are summarized in the Investigator's Brochure.

Omiganan Topical gel [REDACTED] in this protocol, in previously conducted phase 1 and 2 clinical studies, and in other historical documentation is based on the concentration of omiganan pentahydrochloride. The product concentration based on the active moiety is omiganan topical gel [REDACTED]. To be consistent with the naming convention in pre-existing documents, the nomenclature concentration of omiganan [REDACTED] will be referred to in this protocol and associated clinical and non-clinical documents.

[REDACTED]

Further, in order to comply with USP General Chapter <1121> Nomenclature to express the strength of the drug product based upon the active moiety, [REDACTED]

[REDACTED]

5.2 RATIONALE

To date, the safety of omiganan pentahydrochloride topical gel [REDACTED] has been evaluated in subjects exposed to treatment for 12 weeks. This study is being conducted to meet recommendations of ICH-E1a and FDA guidance that 300 subjects be exposed for 6 months and 100 subjects exposed for one year to evaluate the long term safety of drugs intended for long-term treatment (chronic or repeated intermittent use for longer than 6 months). This study is designed contribute up to 300 of the required 300 subjects exposed for 6 months and up to 100 subjects exposed for one year. The Phase 3 Pivotal study (CLS001-CO-PR-004) has an open label extension phase which is designed to also contribute subjects required to fulfill 300 subjects exposed to study drug for 6 months and 100 subjects exposed for one year. The enrollment and completion of the study participants will be monitored via the electronic data collection system to determine when sufficient numbers of subjects have completed the studies to meet the long term safety exposure requirements.

6 STUDY OBJECTIVES

The primary objective of this study is to evaluate the long-term safety of omiganan topical gel applied once daily to the face of subjects with papulopustular rosacea.

7 INVESTIGATIONAL PLAN

7.1 OVERALL STUDY DESIGN

This study will be conducted in accordance with the FDA and ICH guidelines on current GCP, and following the ethical principles originating from the Declaration of Helsinki. Additionally, the study will be conducted in accordance with any applicable laws or regulations of the country in which the clinical research is conducted.

The study will be conducted as an open-label, multicenter study at approximately 35 sites in the United States, Canada, , France, Netherlands, United Kingdom, Sweden, Australia and New Zealand and involving approximately 300 subjects with severe papulopustular rosacea. After giving informed consent, each subject will be screened for study eligibility according to specific inclusion/exclusion criteria. Eligible subjects will be enrolled to evaluate the long-term safety of omiganan topical gel. Omiganan gel will be topically applied once daily to the entire facial area; cheeks, chin, forehead and nose, avoiding contact with the eyes, mouth, and inside the nose.

Following baseline testing and evaluation for acceptance into the study, eligible subjects will be supervised during the first test drug application on Day 1 to ensure that the study treatment is applied correctly. Thereafter, each subject will apply the study treatment at home (unsupervised) once daily for up to 12 months. Once 100 subjects have completed

CONFIDENTIAL

Version Date: 07 March 2017

one year and 300 subjects have completed 6 months of treatment with omiganan topical gel (in the CLS001-CO-PR -004 and -006 studies combined), the remaining subjects in this study will discontinue treatment and will have their final study visit performed and no additional subjects will be recruited.

Other concurrent therapies will be recorded throughout the study. A bland non-medicated soap or soap less cleanser should be used throughout the study for the purposes of washing the subject's face.

Safety assessments will be done on all of the designated study visit days. The end of the study will be the date that the last study subject completes the last visit for the study.

7.2 SELECTION OF STUDY POPULATION

7.2.1 Inclusion Criteria

Subjects must meet each of the following criteria to be considered eligible for entry into the study:

1. Subjects who have provided written informed consent to participate in the study.
2. Healthy, male and nonpregnant female subjects, 18 years of age or older.
3. A diagnosis of severe papulopustular rosacea using the Investigator Global Assessment (IGA) grading scale (Grade 4; described as numerous (≥ 20) small and or large inflammatory papules/ pustules, and up to 2 nodules, (at baseline))
4. Subjects with the presence of telangiectasia at Baseline
5. Subjects with the presence of facial erythema associated with their rosacea at Baseline
6. Non-nursing, female subjects of child bearing potential, who are using a highly effective form of birth control or females not of childbearing potential due to menopause (must be postmenopausal for at least one year).
 - Highly effective methods of birth control are defined as those, alone or in combination, that result in a low failure rate (i.e. less than 1% per year) when used consistently and correctly. Forms of birth control include: Oral (birth control pills), Intravaginal: (e.g. NuvaRing®), Implantable (e.g. Norplant®), injectable (e.g. Depo-Provera®) or transdermal (e.g. Ortho Evra®) contraception; intrauterine device (IUD); double-barrier (diaphragm or condom with spermicidal gel or foam); for two months prior to study enrollment or a vasectomized partner or true abstinence (in line with preferred and usual lifestyle of subject) with an acceptable form of birth control should

CONFIDENTIAL

Version Date: 07 March 2017

the subject become sexually active. Periodic abstinence (e.g., calendar, ovulation, symptothermal, post-ovulation methods) and withdrawal are not acceptable methods of contraception. All female subjects of child bearing potential must undergo an in-office, highly sensitive urine pregnancy test, with a negative result, prior to receiving study drug. In addition, women of childbearing potential must agree to have a highly sensitive urine pregnancy test at the end of the study.

7. Subjects who are willing and able to return to the study clinic for the designated study visits.
8. Subjects who are willing to refrain from sunbathing, using sun tanning booths/beds, or excessive exposure to the sun for the duration of the study.
9. Subjects who are willing to comply with the protocol and visit requirements.

7.2.2 Exclusion Criteria

Subjects are not eligible to participate in the study if any of the following are present:

1. Subjects with clinically significant abnormal findings at the Screening or Baseline/Day 1 Visit that would require a new intervention or treatment or a change in treatment that would in the opinion of the investigator supersede participation in the clinical trial.
2. Subjects with steroid rosacea or subtype 3 (phymatous rosacea).
3. Subjects with nodular rosacea (defined as more than 2 lesions greater than 5 mm).
4. Subjects with underlying diseases or other dermatological conditions, such as; atopic dermatitis, perioral dermatitis, or seborrheic dermatitis, which requires the use of interfering topical or systemic therapy or may interfere with the rosacea diagnosis or its assessment.
5. Subjects with known allergies to the active ingredient or any of the excipients. (See Section 7.5.2)
6. Subjects who have not undergone the specified washout period(s) for the following topical preparations applied to the face or subjects who require the concomitant use of any of the following topical preparations/treatments applied to the face:

Product Washout Period
(Prior to Baseline/First Dose)

- Abradants, astringents, toners, facials, masks, or moisturizers containing retinols, AHA (alpha hydroxyl acids), salicylic acids
 - Tanning booths/beds 1 week
 - Antibiotics (other than topical ocular application) 2 weeks
 - Antimicrobial soaps 2 weeks
 - Corticosteroids 2 weeks
 - Other anti-inflammatories 2 weeks
 - Other rosacea treatments (e.g., azelaic acid, metronidazole, ivermectin, sulfacetamide) 2 weeks
 - Retinoids 4 weeks
7. Subjects who have not undergone the specified washout period(s) for the following systemic treatments or subjects who require the concomitant use of any of the following systemic treatments:

Product Washout Period
(Prior to Baseline/First Dose)

- Antibiotics 4 weeks
 - Corticosteroids 4 weeks
 - Retinoids 4 weeks
8. Female subjects who are pregnant, nursing, or planning a pregnancy within the study period.
9. Subjects using an investigational drug within 30 days of the Baseline Visit or who are currently participating in an investigational study. Use of an investigational drug/device and/or participation in another investigational study is prohibited during this study.
10. Subjects who currently abuse alcohol or drugs or who have a history of chronic alcohol or drug abuse with in the past year.
11. Subjects who have a chronic medical condition that may require the use of a prohibited medication to treat new symptoms or exacerbations, for example, rheumatoid arthritis.

7.2.3 Withdrawal from Study Criteria

Reasons for discontinuation of study medication include, but are not limited to, the following:

- Adverse Event
- Pregnancy

- Withdrawal By Subject
- Lost To Follow-Up. The Investigator will try to reach the subject, twice by telephone (document telephone calls) and once by certified letter, before considering the subject lost-to-follow-up. The lost to follow-up discontinuation will be reported on the appropriate eCRF, and a copy of the letter sent to the subject will be maintained in the Investigator's file.
- Study Terminated By Sponsor
- Physician Decision
- Non-Compliance with Study
- Other

All premature discontinuations of study medication must be documented by the Investigator on the eCRF, and if due to an adverse event, on the Adverse Event Case Report page of the eCRF. All subjects should attempt to complete all visits and evaluations.

Subjects not completing the entire study should be fully evaluated (i.e., final visit procedures performed). All subjects are free to withdraw from participating in this study at any time and for whatever reason, specified or unspecified, and without prejudice to his or her medical care by a physician.

7.3 CONDUCT OF STUDY

7.3.1 Table of Study Procedures

Procedures	Screening (Within 30 days of Baseline)	Baseline (Day 1)	Interim Visits: Month 1, 3, 6, and 9 (Week 4, 12, 26 and 39 ± 14 days) or Unscheduled Visit	Final Visit: Month 12/EOT (Week 52 ± 14 days)
Informed Consent	X			
Demographics, Medical and Rosacea History	X	X		
Limited Physical Exam including weight	X (including height)			X
Vital signs	X		X (Month 6 only)	X
Blood collection for Clinical Laboratory Test (hematology, chemistry)	X			X
Blood collection for immunogenicity testing		X	X	X
Urine Pregnancy Test, if applicable	X			X
Investigator Global Assessment	X	X	X	X
Inclusion/Exclusion Criteria	X	X		
Weigh Tubes/Dispense Study Drug		X	X	
Dispense Diaries		X	X	
Collect Diaries			X	X
Instruct on Treatment Application		X	X	
Apply Study Drug		X	X	X
Collect drug/ Drug Accountability/ Compliance check			X	X
Previous/Concomitant Medication/Therapy Review	X	X	X	X
Adverse Event Assessment		X ¹	X	X

¹ Adverse event assessment during the Baseline visit will be performed following the first application of study drug.

CONFIDENTIAL

Version Date: 07 March 2017

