7.3.2 Study Procedures by Visit

Visits following the Baseline Visit are to occur at Months 1, 3, 6, 9, and 12 at Week 4, 12, 26, 39 and 52 (Final Visit). Interim study visits and the Final Month 12 (Week 52) study visit may be conducted (on an individual subject basis) up to 14 days before or after the regularly scheduled study visit. An unscheduled visit may occur in the event that the investigator determines that the subject should be seen for safety reasons.

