Have the subject record the first application of study drug in the diary during the site visit and confirm their understanding of the use of the diary.

After the first application of study drug at this visit -

- Observe the subject for any immediate adverse events.
- Remind the subject about restricted therapies (see Section 7.5.9.1).
- Remind the subject to contact the investigator if he/she experiences any adverse events.
- Remind the subject that the study drug tubes are not to be discarded and that the drug tubes must be returned to the site at the next study visit. Subjects should be instructed to immediately report lost tubes to the site.
- Remind the subject to apply the study drug once daily, as directed, preferably in the morning.
- Remind the subject to record their study drug application in the diary each day during the study and to use the gel from one tube before opening a new tube.
- Remind the subject to return the diary to the site at the next study visit.
- Remind the subject to follow the treatment application instructions.
- Schedule the next visit.

7.3.2.3 Interim Visits at Months 1, 3, 6, and 9 (Weeks 4, 12, 26 and 39 ± 14 days)

- Question the subject and record any new or changes in adverse events.
- Question the subject about any new or changes in concomitant medications/therapies.
- Obtain a blood sample for immunogenicity testing
- Perform the Investigators Global Assessment (IGA) of rosacea. **Every effort should be made to maintain consistency of the evaluator for each subject.**
- Vital signs will be measured (Month 6 Visit ONLY)
- The subject should apply the study drug at the study site under supervision of appropriate site personnel
- **Treatment Compliance Check** - Collect the study diary to perform a treatment application compliance review. Check compliance by reviewing the number of treatment applications in the diary to determine if there are missed doses. The subject should be re-instructed on study drug application, if compliance is an issue.

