- **Dispensing and Return of Study Treatment** - No new study drug supply will be dispensed at the Month 1 visit; the drug tubes which were dispensed to the subject at Baseline should be returned to them at the Month 1 Visit after completing the treatment application check (unless the tube is empty; then it should be retained at the site and weighed). Record the date of dispensing and subject number on each tube label. **Weigh returned tubes.** The dispensing and return information should be recorded on the source document. Collect the previous diary and dispense a new diary to the subject at the Month 1, 3, 6, and 9 Visits. The diary should be collected at each visit.
- Remind the subject about restricted therapies (see Section 7.5.9.1).

CONFIDENTIAL

Version Date: 07 March 2017

- Remind the subject to apply the study drug once daily, as directed, and record their daily treatment application in their diary.
- Remind the subject to contact the investigator if he/she experiences any adverse events.
- Remind subject that the study medication tubes are not to be discarded and all must be returned to the site at the next study visit. Remind them to notify the site immediately if they have lost a tube.
- Remind the subject to return the diary to the site at the next study visit.
- Remind the subject to follow the treatment application instructions.
- Schedule the next visit

7.3.2.4 Final Treatment Visit at Month 12/End of Treatment Visit (Week 52 ± 14 days/EOT Visit)

- Question the subject and record any new or changes in adverse events.
- Question the subject and record any changes or additions to concomitant medications/therapies.
- Perform the Investigators Global Assessment (IGA) of rosacea. **Every effort should be made to maintain consistency of the evaluator for each subject.**
- Perform a limited Physical Exam with vital signs, and weight measurement
- **Obtain a blood sample for immunogenicity testing**
- Obtain a blood sample for hematology and chemistry analysis
- Perform an in-office urine pregnancy test on all females of child-bearing potential.
- The subject should apply the study drug at the study site under supervision of appropriate site personnel

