7.4.2 Limited Physical Exam

A limited physical exam, will be performed at the Screening Visit (including height and weight) and at the final Month 12 Visit (End of Treatment Visit or Early Termination Visit), including weight will be performed. The limited Physical Exam should include an assessment of the following:

- General Appearance
- Head
- Eyes

CONFIDENTIAL

Version Date: 07 March 2017

- Ears
- Nose
- Throat
- Lungs
- Heart
- Skin

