7.4.3 Vital Signs

Vital signs (blood pressure, respirations, heart rate) will be measured at the Screening Visit, Month 6 and Month 12 (Final or Early Termination) Visit.

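### The schedule calls for on-site study drug application at the Final/EOT visit and at unscheduled visits, with no exemption for subjects taken off drug

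*Protocol*

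**What the plan says.** The Table of Study Procedures (protocol 7.3.1) puts unscheduled visits in the same column as the interim visits: "Interim Visits: Month 1, 3, 6, and 9 (Week 4, 12, 26 and 39 ± 14 days) or Unscheduled Visit". The row for applying study drug has a plain mark there and another in the Final Visit (Month 12/EOT) column. Neither mark has a footnote or condition.

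The text for the scheduled interim visits (7.3.2.3) and for the Final/EOT visit (7.3.2.4) gives the same instruction: "The subject should apply the study drug at the study site under supervision of appropriate site personnel".

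On unscheduled visits, 7.3.2 says: "An unscheduled visit may occur in the event that the investigator determines that the subject should be seen for safety reasons". It does not list the procedures for such a visit.

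On early stopping, 7.2.3 lists adverse event and pregnancy first among the reasons for discontinuing study medication, and then says: "Subjects not completing the entire study should be fully evaluated (i.e., final visit procedures performed". Section 7.4.6 requires that a subject who becomes pregnant be withdrawn.

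**The concern.** Two groups of subjects come to visits where the schedule calls for a supervised dose, although dosing them is either ruled out or in doubt. The first group has stopped drug early and attends for the final procedures, possibly because of a reaction or a pregnancy. The second attends an unscheduled visit because the investigator has a safety reason to see them.

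For a subject stopped for a reaction, the dose would be an unplanned re-exposure. Section 7.4.7.2 names re-challenge as evidence for the strongest category of relatedness, so such a dose could also affect the causality assessment. For a subject withdrawn for pregnancy, the dose serves no purpose. Observation for immediate events after application is written only for the Baseline visit, and no routine visit follows Final/EOT. A new reaction to a dose given there would therefore have no scheduled contact at which to be found. Long-term safety is the study's only stated objective, so the instruction should be right even if few subjects are affected.

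**Working it through.** The plan gives no figure on this point, and none is needed. The check sets the sections side by side.

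**Step 1. Where post-baseline application is instructed**

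| Visit type | Table 7.3.1 | Visit text | Condition for subjects off drug |
|---|---|---|---|
| Scheduled interim (Months 1, 3, 6, 9) | marked (shared column) | 7.3.2.3, yes | none |
| Unscheduled | marked (same shared cell) | none; 7.3.2.3 is headed for Months 1, 3, 6 and 9 only | none |
| Final/EOT | marked | 7.3.2.4, yes | none |

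That is 2 table cells + 2 sentences = 4 distinct places, and 0 carry a condition. The 7.3.2.3 sentence covers only scheduled interim visits, where a supervised dose for a continuing subject is unremarkable. The visits in question therefore rest on 3 places: the table cell and the sentence for Final/EOT, and the shared cell for unscheduled visits.

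**Step 2. Whether the authors state conditions where they intend them**

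They do. The pregnancy test row reads "Urine Pregnancy Test, if applicable", and vital signs in the shared column are limited to Month 6. Dispensing is marked without exception in that column, but the visit text corrects it: "No new study drug supply will be dispensed at the Month 1 visit". For application at Final/EOT, the visit text repeats the mark and does not limit it.

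**Step 3. Who attends the Final/EOT visit**

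Section 7.2.3 sends every non-completer through the final visit procedures. The assessment sections treat the final visit as the early termination visit too: physical exam, "at the final Month 12 Visit (End of Treatment Visit or Early Termination Visit" (7.4.2), and vital signs, "Month 12 (Final or Early Termination) Visit" (7.4.3). Sections 7.4.4 and 7.4.6 do the same for laboratory and pregnancy tests. Section 7.2.3 also asks all subjects to try to attend all visits, so a subject off drug might come to a scheduled interim visit as well.

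**Step 4. Comparison with the stopping rules**

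Discontinuing study medication (7.2.3) and withdrawal for pregnancy (7.4.6) both mean no further dosing. Steps 1 and 3 together call for one more dose. Neither section says that application is left out of the final procedures. Section 7.3.2.4 includes a pregnancy test but does not make application depend on its result.

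**Step 5. Whether any other section resolves the conflict**

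No section of the protocol or SAP exempts subjects who are off drug. Section 8.5 tells investigators to follow the protocol exactly, and 8.2 requires written approval for changes in conduct. A site that sensibly withholds the gel therefore departs from the listed procedures.

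**Step 6. Same-day dosing**

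Subjects dose at home once daily, preferably in the morning. Neither the visit reminders nor Appendix A tells them to hold the dose on a visit day. The on-site instruction can therefore add a second dose on that day, and the same footnote can prevent this.

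**The case against.** The strongest reply is that the conflict appears only on an over-literal reading. Section 7.2.3 asks that early stoppers be evaluated, and applying gel evaluates nothing. The specific rules on discontinuation and pregnancy already imply no further dosing, and the application sentences are worded as what the subject should do, not must do. The four sections that name early termination do so for physical exam, vital signs, laboratory tests and the pregnancy test; none does so for application. The shared table column also marks dispensing and re-instruction, which presume a subject who is continuing treatment, so it reads as a summary.

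Much of this stands. It is the reason to expect that most investigators would withhold the gel and that few subjects, if any, would be dosed wrongly. The link from early stopping to application does depend on the general parenthesis in 7.2.3 combined with 7.3.2.4.

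A reader might also infer that the visit text orders dosing at unscheduled visits. It does not: 7.3.2.3 is limited to the four scheduled months, and 7.3.2 lists no procedures. That part of the point has a single table cell behind it.

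The reply does not remove the instruction. It asks the investigator to infer an exception that no section states, under a protocol that asks for exact adherence.

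**Conclusion.** The point holds as a conflict within the written schedule. At Final/EOT, the table and 7.3.2.4 call for a supervised dose without condition, and 7.2.3 brings early stoppers into that visit. At unscheduled visits, one table cell does the same. Followed literally, this would dose a subject already taken off drug or being seen for a possible reaction.

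The expected impact is small. That judgement assumes that most investigators would withhold the gel; the documents give no number of subjects affected.

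A reader might infer that the extra dose biases the days-of-exposure summary (protocol 7.6.9, SAP 4.3.4) by moving the date of last application to the visit day. The documents do not support that claim. Neither defines days of exposure, and neither gives the number of subjects stopped for these reasons or their gap before the final visit. Suppose exposure is counted from first to last application, k of 300 subjects are affected, and each gains g days. The mean then shifts by k × g / 300. With assumed ranges of k = 3 to 30 and g = 1 to 14, the shift runs from 3 × 1 / 300 = 0.01 days to 30 × 14 / 300 = 1.4 days, against treatment of up to 52 weeks. Missed applications and the discontinuation itself are recorded on the eCRF (7.5.1, 7.2.3), so an off-drug gap should be recoverable. No hypothesis test depends on it. The case for a change rests on subject protection and clear instructions.

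**What to change.** Add one footnote to the study drug application row of Table 7.3.1, in both post-baseline columns, and put matching words in 7.3.2.3 and 7.3.2.4:

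*Do not apply at an early termination visit or at any visit after study drug has been discontinued (e.g., for an adverse event or pregnancy). At an unscheduled visit, apply only if the investigator judges that the subject should continue study drug. Do not apply if that day's dose has already been taken.*

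The condition should not be worded simply as continuing on study drug. Nobody continues after Month 12, so that wording could bar the last dose for every completer. With the text above, subjects who complete Month 12 on treatment still apply their final dose.

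The cost is one footnote and the same words in two visit sections at the next amendment, with no added visits, tests or data fields.
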